**Version 4.0**

**7 October, 2020**

## **1. Background and rationale:**

Pregnant and breastfeeding women in South Africa are at very high risk of HIV acquisition and vertical HIV transmission during pregnancy, labour and breastfeeding. One-third to half of perinatal HIV transmission occurs in women who are seroconvert during the pregnancy and post-partum period. Effective use of pre-exposure prophylaxis (PrEP) could contribute to eliminating maternal HIV acquisition, and hence mother to child transmission (MTCT) of HIV. However, PrEP efficacy requires high levels of adherence, and adherence requires high levels of acceptability, yet there are few data on how best to promote adherence to PrEP in postpartum women.

We propose to conduct a pilot study of the feasibility and acceptability of an adherence promotion package in n=200 postpartum women enrolled in an ongoing PrEP study (PrEP-PP; ongoing, HREC Ref 297/2018; PI [name]) to evaluate the feasibility, acceptability and efficacy of a package of interventions to improve PrEP adherence in pregnancy and postpartum women. Specifically the package of interventions will include:

- (1) SMS/Whatsapp messages with reminders about PrEP,
- (2) HIV self-testing (for the participant and her partner) and
- (3) immediate feedback on PrEP adherence using a urine lateral flow assay that tests the level of tenofovir taken in the past 48 hours.

The sub-study will take place in Gugulethu Midwife Obstetric Unit (MOU). We will enroll n=200 HIV-uninfected postpartum women (1-6 months postpartum) at their regular PrEP-PP study visit and follow them for 1 month. We will randomize 1:1 to the intervention arm (n=100) to compare with the standard of care arm. The adherence promotion intervention package will include provision of a HIV self-test for the woman and her partner, SMS messaging about PrEP taking, and adherence based feedback following the urine lateral flow assay (that measures recent tenofovir in past 48 hours). In the standard of care arm, n=100 will receive standard of care PrEP-PP services including: HIV counseling and testing in the facility by the PrEP study staff, face-to-face counseling that is based on self-reported adherence, without any SMS interventions or urine assay.

At baseline and endline (1 month) we will administer a brief 15-20 minute survey about recent PrEP adherence in the standard of care and intervention groups, and feasibility and acceptability of the package of interventions in the intervention group. Participants will receive an option to participate in the interview on the phone instead of returning to the health facility.

Outcomes include a comparison of objective PrEP adherence using tenofovir measure in the urine assay at 14 and 30 days following baseline. We will analyze the survey responses to evaluate acceptability and feasibility alongside the efficacy data to inform the development of a larger randomized control trial in postpartum women.

**COVID-19 and study implications.** Our PrEP-PP study (HREC Ref 297/2018) has continued during the COVID-19 lockdown in South Africa as PrEP provision is considered to be an essential service. We continue to effectively and safely recruit ~15 women/week and ~20 retention visits/week during the COVID lockdown and observe all UCT and Department of Health infection prevention and control methods. The proposed intervention is designed to promote adherence to PrEP in high risk postpartum

women, whilst minimising contact with the health facility, healthcare workers and study staff through HIVST, phone based SMS counselling, and phone interviews.

## **2. Study objectives:**

The objectives of the proposed pilot sub-study are to evaluate the feasibility and acceptability of a package of interventions to improve PrEP adherence in postpartum women.

1. Evaluate acceptability and feasibility of adherence promotion package in women randomized to the intervention arm including:
  - a. SMS: # of messages received, # responded to, feedback from women about responses to messages and utility in improving adherence
  - b. HIV self-testing in women and their partners: # of women who report self-testing at home, and # who report their partners testing (and test results), and feedback from women in surveys about their experience with using self-tests for themselves and partners, and feasibility as reported by study staff to explain HIVST in their counseling
  - c. Integrating urine based lateral flow assays in reporting back adherence levels to PrEP in women: Measured by the time the test takes, correlation with self-reported recent adherence, the feasibility as reported by study staff to read the test and feedback from the woman about the satisfaction and understanding following the bio-feedback
2. Evaluate objective PrEP adherence levels following intervention and compare with standard of care arm:
  - a. Evaluate tenofovir levels in urine assay at 2 weeks and 4 weeks following baseline intervention in intervention arm and compare with standard of care arm at 1 month

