**Table 1. Sub-study list of visits and assessments per arm**

Visit	Intervention Arm	Standard of care Arm
Baseline	1. ICF for sub-study 2. Survey 3. HIV self-test for self and partner with counselling 4. Urine TDF test with adherence based counselling	1. ICF for sub-study 2. Survey 3. Invitation for partner testing 4. Urine TDF test (no counselling or feedback)
30 days	1. Endline survey 2. Urine TDF test with adherence based counselling	1. Endline survey 2. Urine TDF test (no counselling or feedback)

**Intervention arm:** Consented, enrolled women in the intervention group (n=100) will receive an adherence promotion intervention package that includes the following visits/assessments:

1. **At baseline:**

- a. HIV self-test for herself and her partner(s) with instructions on how to use, and instructions on how to report the result to the study on the SMS/Whatsapp messages.

- b. Adherence based counseling and feedback from a urine tenofovir test (that measures recent tenofovir in past 48 hours)
- 2. **Weekly:** SMS messaging with counseling and reminders about taking daily PrEP
- 3. **At 2-weeks (extra visit- not part of standard of care):** adherence based feedback and counseling following the urine lateral flow assay

**Standard of care arm:** In the standard of care arm, women will receive normal PrEP-PP services as per study protocol including facility based HIV testing and counselling with a letter to refer their partner for testing in the facility. Women in the standard of care PrEP-PP arm will not receive SMS reminders or messages, nor will they get feedback following the urine assay on their tenofovir levels. Participants will receive standard counselling about importance of adherence, prescription for 3 months of PrEP, and invitations for the study appointment in 4 weeks' time.

**Baseline and endline adherence evaluation (both arms):** All participants, regardless of study arm, will receive urine lateral flow testing of tenofovir levels at baseline and again at 1 month.

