**Baseline and endline survey (both arms):** At baseline and endline (1 month) we will administer a brief 15-20 minute survey about recent PrEP adherence in the standard of care and intervention groups, and feasibility and acceptability of the package of interventions in the intervention group. A trained study staff will ask the survey questions in isiXhosa using RedCap. Participants will receive an option to participate in the interview on the phone instead of returning to the health facility.

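### Objective 1c relates the urine assay to self-report only by a correlation, with no visit named and in one arm; a baseline cross-tabulation in both arms would show how many self-reported users test urine-negative

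*Combined protocol and SAP*

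**What the plan says.** Section 2 opens Objective 1 with a stem that fixes the population: "Evaluate acceptability and feasibility of adherence promotion package in women randomized to the intervention arm including". Item 1c under it concerns "Integrating urine based lateral flow assays in reporting back adherence levels to PrEP in women". It lists several measures: how long the test takes, how feasible staff find reading it, women's satisfaction and understanding, and "correlation with self-reported recent adherence". The last is the only measure that sets the assay against self-report. No coefficient, cut-off or visit is given, and no analysis of urine result against self-report appears elsewhere in the text.

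Section 4 schedules both measures in both arms. On the assay: "All participants, regardless of study arm, will receive urine lateral flow testing of tenofovir levels at baseline and again at 1 month". On self-report, the baseline and endline questionnaire is a "survey about recent PrEP adherence in the standard of care and intervention groups". The visit table in section 4 lists the baseline survey ahead of the urine test in each arm.

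The arms differ in what follows the test. Intervention women are counselled on the result at baseline, and at 2 weeks receive "adherence based feedback and counseling following the urine lateral flow assay". Standard of care women have the test, "nor will they get feedback following the urine assay on their tenofovir levels".

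**The concern.** A correlation measures association. For planning the larger trial, the useful quantity is how often a woman says she is using PrEP while the assay finds no tenofovir. Section 1 says that standard counselling rests on self-report and that the package adds assay feedback, so this share describes what the assay adds. A correlation printed on its own does not give it, and treats disagreement in either direction alike.

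The unstated visit adds a second problem. By 1 month, intervention women have twice been counselled on their own assay result, which may change what they report. An estimate that does not name its visit could mix reports made before and after feedback.

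The arm limit suits test time, staff reading and satisfaction, because results are fed back only in that arm. It is not needed for the self-report comparison, where it would set aside half of the planned baseline pairs.

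**Working it through.** The plan states no expected correlation, positivity rate or precision target for 1c, so there is no figure to reproduce. From section 1: 200 women randomised 1:1, hence 100 per arm. All cell counts and rates below are assumptions, as is a yes/no reading of both measures.

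**1. What a correlation leaves open.** Write a table as (report+/urine+, report+/urine-, report-/urine+, report-/urine-) = (a, b, c, d).

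- Phi = (ad - bc) / sqrt[(a+b)(c+d)(a+c)(b+d)].
- Share urine-negative among reporters = b/(a+b).
- Percent agreement = (a+d)/200.

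Table A (100, 40, 4, 56):
- phi = (5,600 - 160) / sqrt(140 × 60 × 104 × 96) = 5,440 / 9,157.8 = 0.594
- urine-negative among reporters = 40/140 = 28.6%
- agreement = 156/200 = 78%

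Table B (100, 4, 40, 56):
- phi = (5,600 - 160) / sqrt(104 × 96 × 140 × 60) = 0.594
- urine-negative among reporters = 4/104 = 3.8%
- agreement = 156/200 = 78%

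In A most disagreement is report without drug; in B it is drug without report. Phi does not separate them, and neither does percent agreement, so the directional share should lead.

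If every woman reports use, as in (120, 80, 0, 0), phi is undefined while 80/200 = 40% are urine-negative. Near-universal reporting is conceivable because entry requires being on PrEP (section 3, inclusion criteria).

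**2. What the second arm adds at baseline.** Assume 80% of pairs report use and 20% of those are urine-negative. The Wilson 95% interval for proportion p in m reporters, with z = 1.96, is [p + z²/2m ± z·sqrt(p(1-p)/m + z²/4m²)] / (1 + z²/m).

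| Pairs | Urine-negative / reporters | 95% CI |
|---|---|---|
| 100 (one arm) | 16/80 | 12.7-30.0% |
| 200 (both arms) | 32/160 | 14.5-26.9% |
| 80 (one arm, 20% of pairs lost) | 13/64 | 12.3-31.7% |
| 160 (both arms, 20% of pairs lost) | 26/128 | 14.3-28.1% |

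With full data the interval width falls from 30.0 - 12.7 = 17.3 points to 26.9 - 14.5 = 12.4 points, a ratio of 0.72, close to 1/sqrt(2).

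**3. Why baseline is the clean visit.** The baseline survey is listed before the first urine test, so neither arm has yet had sub-study feedback and the arms can be pooled. At 1 month one arm has had feedback twice and the other not at all, so results there should be kept apart by arm.

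**4. Whether the both-arm data exist.** Section 4 (text and visit table) and the timeline table put the urine test in all participants, and Objective 2a compares the arms on it at 1 month. Section 1, however, describes the standard of care arm as having no urine assay. It may mean no feedback, but it does not say so.

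**The case against.** The strongest reply is that item 1c lists feasibility measures for the arm that receives feedback and is not an analysis specification. On that view, correlation may be loose wording for comparison, and a cross-tabulation in all women answers a different question. This has force for the feasibility items, which should stay as they are. For the self-report measure, the plan does not say that agreement is meant, and one sentence would settle it.

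A second reply is that, on a yes/no reading, phi together with the two marginal percentages determines the share exactly. In Table A, 70% report use and 52% are urine-positive. The joint proportion is therefore 0.70 × 0.52 + 0.594 × sqrt(0.70 × 0.30 × 0.52 × 0.48) = 0.500, and 1 - 0.500/0.70 = 28.6%. This is correct, and it limits the point to a correlation reported without its margins. The plan does not promise baseline margins for 1c, so the point is weakened but remains.

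A third is that the gain in precision is modest and no decision rule depends on it. That also stands, and it keeps the point minor.

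A reader might go further and infer that the table would reveal over-reporting. The documents do not support that. Section 1 describes "a urine lateral flow assay that tests the level of tenofovir taken in the past 48 hours", while the survey asks about recent adherence with no recall window stated. A urine-negative woman may have taken PrEP earlier than the assay can see, and assay error adds further disagreement.

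**Conclusion.** The point holds as a cheap improvement. Objective 1c offers only a correlation, names no visit and is confined to one arm, although both measures are planned in both arms at baseline and 1 month. A correlation alone can be identical (0.594) when 28.6% or 3.8% of reporters are urine-negative. Using both arms at baseline would narrow the 95% interval by about 28% under the stated assumptions.

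The example tables show what is possible; they do not predict this cohort. The size rests on an assumed yes/no readout and assumed rates, and on the standard of care urine test taking place as section 4 says. The survey items are not in the text supplied, so whether one already matches the 48-hour window cannot be checked.

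Nor should a reader infer that the trial's adherence comparison is compromised: Objective 2 compares urine results between arms and does not use self-report. This is a secondary descriptor in a pilot.

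**What to change.** - Keep test time, staff reading and satisfaction as intervention-arm measures.
- Replace or supplement the correlation with a baseline cross-tabulation of self-report by urine result in all randomised women with paired data (up to 200). Report percent urine-negative among self-reported users, with a 95% CI and the number of pairs, and percent agreement as a secondary figure.
- If either measure is not read as yes/no, use the graded equivalents: percent reporting above their assay level, and weighted agreement.
- Use the self-report item closest to the 48-hour window, and label the result discordance.
- Show 1 month separately by arm, using surveys and urine samples paired in time. Record both dates, because the survey may be done by phone.
- Reconcile section 1's statement that the standard of care arm has no urine assay with section 4 and the timeline table, since the both-arm table depends on it.

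The cost is a little more analysis of data already planned, and one recall item if the survey lacks one near 48 hours. No visits or urine tests are added.

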## **3. Study design**

Randomized control pilot sub-study of n=200 postpartum women in the PrEP-PP study.

### Inclusion Criteria:

1. Currently enrolled in PrEP-PP study and on PrEP
2. 18+ years old
3. confirmed HIV-negative (confirmed with a 4th generation antigen HIV test)
4. confirmed to be postpartum (1-6 months postpartum)
5. confirmed to currently have a male partner
6. confirmed to have a cell phone that can read and respond to SMS/Whatsapp messages
7. without psychiatric or medical contraindications to PrEP

### Exclusion criteria: Failure to meet all of inclusion criteria

Eligible, consenting women will receive up to R120 in grocery vouchers and transportation costs, and refreshments for their time and effort in the study at baseline and each follow up visit (1 visit for standard of care arm, 2 visits for intervention arm).

Procedures for the informed consent process are outlined below. Throughout, trained study staff will ensure that women are aware of their right to refuse and/or withdraw from the study at any time. In addition, study staff will emphasize that all study activities are entirely separate from routine postnatal care services received and that refusal or withdrawal from the study will have no impact on their ability to access any services provided at any public-sector health facility.

#### 4. Study procedures

The study will be integrated into the MOU in Gugulethu. Women will be recruited directly from the PrEP-PP study (ongoing, Ref 297/2018). We will not recruit nor enroll new participants, but will draw a sub-sample from our ongoing cohort study. Further, we will not hire new staff, all trained staff are already working in the facility part of the ongoing current PrEP-PP study. The PrEP-PP study recruiter will recruit eligible directly from women in the cohort study, and if interested and eligible after the screening process, the women will go to the study trailer (Green Clinic) in Gugulethu for the sub-study consent and study enrolment procedures.

**Randomization:** We will randomize enrolled PrEP-PP participants who are eligible (see above additional eligibility requirements) and consent to participate in the adherence promotion intervention in a 1:1 ratio to the intervention or standard of care arm. Randomization will be performed using dynamic permuted blocks, with sealed randomization envelopes. The participants will open the envelopes sequentially.

**Table 1. Sub-study list of visits and assessments per arm**

Visit	Intervention Arm	Standard of care Arm
Baseline	1. ICF for sub-study 2. Survey 3. HIV self-test for self and partner with counselling 4. Urine TDF test with adherence based counselling	1. ICF for sub-study 2. Survey 3. Invitation for partner testing 4. Urine TDF test (no counselling or feedback)
30 days	1. Endline survey 2. Urine TDF test with adherence based counselling	1. Endline survey 2. Urine TDF test (no counselling or feedback)

**Intervention arm:** Consented, enrolled women in the intervention group (n=100) will receive an adherence promotion intervention package that includes the following visits/assessments:

1. **At baseline:**

- a. HIV self-test for herself and her partner(s) with instructions on how to use, and instructions on how to report the result to the study on the SMS/Whatsapp messages.

- b. Adherence based counseling and feedback from a urine tenofovir test (that measures recent tenofovir in past 48 hours)
- 2. **Weekly:** SMS messaging with counseling and reminders about taking daily PrEP
- 3. **At 2-weeks (extra visit- not part of standard of care):** adherence based feedback and counseling following the urine lateral flow assay

**Standard of care arm:** In the standard of care arm, women will receive normal PrEP-PP services as per study protocol including facility based HIV testing and counselling with a letter to refer their partner for testing in the facility. Women in the standard of care PrEP-PP arm will not receive SMS reminders or messages, nor will they get feedback following the urine assay on their tenofovir levels. Participants will receive standard counselling about importance of adherence, prescription for 3 months of PrEP, and invitations for the study appointment in 4 weeks' time.

**Baseline and endline adherence evaluation (both arms):** All participants, regardless of study arm, will receive urine lateral flow testing of tenofovir levels at baseline and again at 1 month.

**Baseline and endline survey (both arms):** At baseline and endline (1 month) we will administer a brief 15-20 minute survey about recent PrEP adherence in the standard of care and intervention groups, and feasibility and acceptability of the package of interventions in the intervention group. A trained study staff will ask the survey questions in isiXhosa using RedCap. Participants will receive an option to participate in the interview on the phone instead of returning to the health facility.

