### **Informed consent**

The study informed consent for the study and questionnaire are modelled after that used in previous studies and will be delivered in participants' home language (isiXhosa or Afrikaans) by trained interviewers. This study ICF details the purpose of the study, study procedures, and the risks and benefits to mothers that participants may encounter at the second study visit.

Here, study staff will emphasize to participants that:

- Participation is entirely voluntary, and their choice regarding participation will in no way influence the quality of routine medical care for mothers or their infants
- Women may exit the study at any time for any reason without compromising the quality of health care received.

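### Acceptability ratings are collected aloud by the team that delivers the package, and nothing bars a woman's own counsellor from asking for them, so reported acceptability may be biased upward

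*Combined protocol and SAP*

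**What the plan says.** Section 2 (Study objectives) puts acceptability and feasibility first: "Evaluate acceptability and feasibility of adherence promotion package in women randomized to the intervention arm including" three components, namely messages, HIV self-testing and urine-assay feedback. Each component includes the woman's own opinion. For the urine assay this is "feedback from the woman about the satisfaction and understanding following the bio-feedback"; for messages it is how useful she found them; for self-testing it is her experience with the kits.

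Section 4, under the paragraph on the baseline and endline survey, gives the mode: "A trained study staff will ask the survey questions in isiXhosa using RedCap". The same paragraph restricts the relevant items, on "feasibility and acceptability of the package of interventions in the intervention group", to one arm. The only alternative it offers is a telephone interview.

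On staffing, the opening of section 4 says "we will not hire new staff, all trained staff are already working in the facility part of the ongoing current PrEP-PP study". Objectives 1b and 1c show study staff explaining self-testing in their counselling and reading the urine test. In section 5, the informed consent text says that consent and questionnaire "will be delivered in participants' home language (isiXhosa or Afrikaans) by trained interviewers"; it does not say whether those interviewers also counsel. The table of visits and assessments lists the endline survey and the adherence counselling at the same 30-day visit in the intervention arm.

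**The concern.** A woman who is asked face to face, or by telephone, what she thought of a service by someone from the team that gave it has a reason to be polite. The pull is towards a favourable answer, and it is strongest if the interviewer is the person who counselled her. Two features make this matter here.

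- The error has one direction, so a larger sample does not reduce it; it only narrows the interval around a shifted value.
- The randomised comparison gives no protection. The package items are asked only of women who received the package, so no control-arm answer carries the same bias and could be subtracted.

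Section 1 says that the survey responses, read together with the efficacy data, will inform the design of a larger trial. If courtesy is mistaken for acceptability, that trial may be built around a component that women did not in fact find useful.

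**Working it through.** **Does the plan separate interviewer and counsellor?** The relevant statements, side by side:

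- Section 4 (survey paragraph): the survey is asked aloud by trained study staff.
- Section 4 (opening): no staff are added, and all come from PrEP-PP. Interviewing and delivery therefore draw on one team.
- Section 2, objectives 1b and 1c: study staff counsel and read the assay.
- Section 5 (informed consent): there are trained interviewers, but nothing says they are barred from counselling.
- Section 4 (telephone option): it changes the place of the interview, not who asks.

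Taken together, a shared team is a fair inference. That the same individual does both jobs is neither stated nor excluded.

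**How large could the bias be?** The plan gives no expected acceptability, precision target or bias figure, so there is no number of its own to reproduce. What follows is an illustration.

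Inputs: n = 100 in the intervention arm (section 1). Assumed: true acceptability p of 70%, 80% or 90%; a share b of dissatisfied women who answer favourably of 10%, 25% or 50%; every woman answers the endline survey.

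Formulas:

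- 95% half-width = 1.96 × √(p(1 − p)/100)
- expected reported proportion = p + b(1 − p), so bias = b(1 − p)
- coverage = exact binomial probability, at the reported proportion, that the usual (Wald) 95% interval contains the true p

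Example at p = 80%: half-width = 1.96 × √(0.8 × 0.2/100) = 0.078. With b = 25%, bias = 0.25 × 0.20 = 0.05, so the expected report is 85%.

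| True p | Half-width (points) | Bias, b = 10% | Bias, b = 25% | Bias, b = 50% |
|---|---|---|---|---|
| 70% | 9.0 | 3.0 | 7.5 | 15.0 |
| 80% | 7.8 | 2.0 | 5.0 | 10.0 |
| 90% | 5.9 | 1.0 | 2.5 | 5.0 |

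At a true 80%, coverage is about 93% with no bias (this interval runs slightly under 95% at this n). It falls to about 88%, 65% and 12% for b = 10%, 25% and 50%.

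**When does bias exceed sampling error?** Set b(1 − p) equal to the half-width. At 70%, b = 0.090/0.30, about 30%; at 80%, b = 0.078/0.20, about 39%; at 90%, b = 0.059/0.10, about 59%. A sizeable minority of dissatisfied women, or at 90% a majority, would have to answer against their view before bias outweighed chance. Smaller shares still damage coverage.

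**The case against.** The best case for the plan as it stands has five parts.

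- **Roles may already be separate.** The trained interviewers in section 5 could be a distinct group, and the SOPs in which staff are trained (timeline table, month 1) could allocate interviews. This stands as a reason not to assert that counsellors interview their own clients. It does not remove the gap, because the text reviewed contains no such rule. If the rule exists, stating it takes one sentence.
- **Objective 1 is more than opinion.** It also has message counts, time taken by the test, reported self-test uptake and staff-reported feasibility. This stands: the concern is confined to the women's opinion items. Counts and timings, however, cannot show whether a woman was satisfied or understood her result. Uptake is itself what she tells staff.
- **The bias may be trivial.** At the low end of the assumed range it is 1 to 3 points, well inside sampling error. This stands. A reader might infer a shift of 10 to 20 points; moving a true 70% to 80–90% needs 10/30 to 20/30, or 33% to 67%, of dissatisfied women to reverse their answer. That is the upper part of an assumed range, not an estimate.
- **No decision rule would be crossed.** The plan sets no acceptability threshold for going on to a larger trial. This limits the consequence but does not make the ratings more informative.
- **Spoken interviews are a legitimate choice** where literacy varies. This stands, and is why self-completion is not made a requirement below.

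A reader might also infer that an unbiased route is already on offer, because entry requires each woman to be "confirmed to have a cell phone that can read and respond to SMS/Whatsapp messages". The documents do not support that. The telephone option is still a staff interview, and the messaging channel is planned for reminders, counselling and self-test results. The tools exist; the route does not. Nor do the documents say that the team is small or who hands out the grocery vouchers.

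**Conclusion.** The concern holds in a limited form: a cheap improvement, not a flaw that invalidates the pilot. The plan collects acceptability ratings by spoken interview from within the delivering team, with no stated bar on a woman's own counsellor. Reported acceptability may therefore be too high, and nothing in the randomised design would reveal or offset it.

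On the assumption that 10% to 50% of dissatisfied women answer favourably, the excess is 2 to 10 points at a true 80% and 3 to 15 points at a true 70%, against half-widths of about 8 and 9 points. Those shares are assumptions; the true size could be negligible or could exceed sampling error. It would be too strong to say that the main result is inflated. The urine tenofovir comparison in objective 2 does not depend on who conducts the interview.

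**What to change.** Amend the survey paragraph in section 4 to state that:

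1. the endline opinion items in the intervention arm (satisfaction, usefulness, experience of self-testing, understanding of feedback) are asked, in person or by the existing telephone option, by an existing team member who has not counselled that woman;
2. the interviewer's ID, and whether that person delivered any part of the package, are recorded with each survey;
3. ratings are tabulated by interviewer role. This comparison is descriptive, since interviewers are not allocated at random.

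Factual items can stay with any trained member of staff. Self-completion through RedCap or SMS/Whatsapp may be considered but need not be required: literacy varies, a phone may be shared, and mixing modes within 100 women would tie mode to literacy. In the same edit, reconcile the survey language: section 4 names isiXhosa only, while section 5 names isiXhosa or Afrikaans.

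Cost: a rota rule, two extra fields in the RedCap form (a month 1 build task in the timeline) and somewhat less flexible scheduling. No new staff are needed. Some courtesy towards the team as a whole will remain and should be acknowledged when results are reported.
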